4.4 Outcome Definition and Measures

4.4.1 Safety measures

The frequency, intensity and relationship to treatment will be evaluated for all reported serious adverse events (SAEs) (refer to Section 7.1 for the definition of SAEs).

In addition to SAEs overall, the frequency, intensity and relationship to treatment for the following adverse events of special interest (AESI), both serious and non-serious, will be evaluated:

- Peripheral neuropathy (sensory, motor or other)
- Neutropenia (including febrile neutropenia)
- Infections (including opportunistic infections)
- Hyperglycaemia
- Hypersensitivity reactions (including infusion-related reactions and allergic reactions)

These outcomes will be evaluated in the overall treated population and also specifically within the elderly subpopulation (age at enrolment \geq 65 years) and the population of patients who receive brentuximab vedotin for more than 16 cycles.

Confidential. Page 18 of 44

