The sample size for this study was based on the need for more information regarding the occurrence of AESI, both serious and non-serious, relative to the size of the current safety database. Evaluation of the sample size for the study objectives was performed based on the expected rate of AESI, both serious and non-serious, in patients with relapsed or refractory CD30+ HL or relapsed or refractory sALCL treated with brentuximab vedotin to ensure sufficient enrolment. The targeted sample size of 500 was determined to provide an adequate level of precision to achieve the first safety objective of this study through estimating the proportion of patients experiencing an individual AESI. The sample size of 500 includes the patients already being treated with brentuximab vedotin at the time of enrolment, the retrospective patients. It is assumed that approximately 15 to 20% (75 to 100 patients) of the study population will be retrospectively enrolled.

Interim and Final Analyses:

Details of the statistical analysis will be fully described in a written and approved statistical analysis plan (SAP). Frequency and incidence proportion for all reported SAEs and AESI will be reported for patients enrolled and receiving at least one dose of treatment. Incidence rates and 95% confidence interval (CI) will also be reported for selected events. Time at risk will be defined in the SAP. Analyses will be conducted on the enrolled population, including all patients exposed to brentuximab vedotin. In addition, analyses will be presented separately for patients prospectively and retrospectively enrolled to account for potential differences in the data reported, in particular the volume and nature of adverse events.

Subgroup safety analyses will be performed by indication and other characteristics of interest (e.g., by age at enrolment < 65 or ≥ 65 years, number of treatment cycles). All dose modifications including dose delays, temporary interruptions and permanent interruptions, and reported reason for change(s) will be summarised, and where possible the effect of modifications on safety will be explored.

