In SG035-0003, a phase 2, single-arm, open-label study in patients with relapsed or refractory HL postASCT, and in SG035-0004, a phase 2 trial conducted in patients with relapsed or refractory sALCL, brentuximab vedotin was administered at a dose of 1.8 mg/kg every 3 weeks. One hundred two patients with relapsed and refractory HL and 58 patients with relapsed and refractory sALCL were exposed for a median duration of approximately 27 weeks (9 cycles) and 20 weeks (6 cycles), respectively. The primary endpoint of both studies was overall response rate. Treatment-emergent AEs occurring in $\geq 20\%$ of patients in phase 2 were peripheral sensory neuropathy (44%), fatigue (42%), nausea (41%), diarrhoea (34%), pyrexia (31%), upper respiratory tract infection (28%), neutropenia (21%) and vomiting (20%). These events were primarily mild to moderate in severity and reversible. Approximately half of patients had treatment-emergent peripheral neuropathy, predominantly sensory neuropathy, with an onset and severity pattern consistent with a cumulative effect of exposure. Dose delay and subsequent reduction to 1.2 mg/kg was generally effective in managing peripheral neuropathy. Moderate or severe neutropenia occurred in 13% and 7% of patients, respectively; these events were typically of short duration and well managed by brief dose delays with growth factor support in some cases. Infusion-related reactions occurred in approximately 10% of patients and were typically managed by dose delay or reduction. The clinical laboratory parameters for which the most patients had new or worsening findings were low neutrophils, low lymphocytes, low platelets, low leukocytes and elevated glucose [Younes 2012].

Most patients in the two phase 2 studies were between the ages of 18 and 65 years; as a result, there are limited data available regarding the use of brentuximab vedotin in elderly patients. In addition, the maximum number of cycles administered in the pivotal phase 2 studies was 16 and it is unknown whether there is any change in the safety profile of brentuximab vedotin

Confidential. Page 14 of 44

with longer term use or with the implementation of the recommended dose reductions in the presence of specific toxicities.

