2. RATIONALE

As is common with new therapies for rare conditions, the EMA has required a post-authorisation safety study (PASS) to further evaluate the safety profile of brentuximab vedotin. Specifically, this PASS is designed as a prospective, observational cohort study including patients prescribed brentuximab vedotin as part of routine clinical care and followed for up to five years for the occurrence of selected safety outcomes. In addition to SAEs, the following both serious and non-serious adverse events of special interest (AESI) will specifically be evaluated as part of the PASS: peripheral neuropathy, neutropenia (including febrile neutropenia), infections (including opportunistic infections), hyperglycaemia and hypersensitivity reactions (including infusion-related reactions and allergic reactions). In addition to the overall patient population, to the extent possible, the safety profile of brentuximab vedotin in elderly patients and patients with longer term exposure (i.e., ≥ 16 cycles) will also be evaluated. The study is intended to provide important information regarding the safety profile of brentuximab vedotin in a real-world population.

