Specific studies of brentuximab vedotin in elderly patients have not been conducted and clinical studies did not include sufficient numbers of patients aged 65 and over to determine whether they respond differently from younger patients. Therefore, where possible, relevant subgroup analyses will be performed by age group (i.e., < 65 years and \ge 65 years). Where appropriate, subgroup analysis may also be performed according to the following variables of interest: sex, CD30+ lymphoma type, ALK positivity (sALCL patients), long term treatment (i.e., > 16 cycles) and post-ASCT status. Additional subgrouping may also be applied as described in the SAP.

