5.2.2 Planned analyses

5.2.2.1 Primary analyses

Serious Adverse Events (SAEs) and Adverse Events of Special Interest (AESI)

SAEs and AESI (including both serious and non-serious AESI) will be summarized by MedDRA system organ class (SOC) and preferred term (PT). Frequency and incidence proportion for all SAEs and AESI (as defined in Section 4.4.1) will be reported for patients who received at least one dose of brentuximab vedotin while on study.

The incidence rate and the associated 95% CI will be reported for SAEs and AESI.

Time at risk of SAEs and AESI will correspond to current/recent treatment with brentuximab vedotin. Current/recent treatment will be defined as time between the dates of first and last dose plus 30 days. All other follow-up time accrued for the patient will be considered occurring during past treatment with brentuximab vedotin; events reported during the past treatment period will be presented separately.

In addition, select events will be displayed by timing in relation to treatment start (e.g., by number of completed cycles) or time-to-event analysis may be carried out using Kaplan-Meier plots for the occurrence of the first reported occurrence of the adverse event, as appropriate for the event.

Identification and Description of Risk Factors for Peripheral Neuropathy

In addition, multivariable adjusted analysis will be performed to identify and describe risk factors for peripheral neuropathy (e.g., BMI, previous history of neuropathy, known toxic exposures) in the cohort. Risk factors for the first occurrence of new onset or worsening of peripheral neuropathy will be explored using a multivariable adjusted Cox regression model. Model assumptions concerning proportionality will be evaluated graphically in the usual manner. The inclusion of specific risk factors will be described in the SAP. A preliminary univariate analysis of the association of variables of interest with the outcome measure will be

Confidential. Page 24 of 44

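### Rates in the more-than-16-cycles group count events and time from first dose, so they include 16 cycles free by definition of death and treatment-ending events and do not isolate risk after cycle 16

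*Protocol*

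**What the plan says.** Section 1 sets the question. No patient in the pivotal phase 2 studies had more than 16 cycles, and "it is unknown whether there is any change in the safety profile of brentuximab vedotin" with longer use. Section 2 makes this a named aim, to the extent possible, for "patients with longer term exposure (i.e., ≥ 16 cycles" or more precisely for those at or above that cut-off.

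Section 4.4.1 evaluates the outcomes in "the population of patients who receive brentuximab vedotin for more than 16 cycles". Section 5.2.1 lists "long term treatment (i.e., > 16 cycles) and post-ASCT status" among optional subgroup variables, next to sex and lymphoma type. The synopsis gives as examples of subgroups "by age at enrolment < 65 or ≥ 65 years, number of treatment cycles".

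Section 5.2.2.1 sets the measures: frequency, incidence proportion and rate ("The incidence rate and the associated 95% CI will be reported for SAEs and AESI"). It also sets the clock: "Current/recent treatment will be defined as time between the dates of first and last dose plus 30 days". No other start of risk is given for the long-term group. The same section allows selected events to be shown by completed cycles, or by Kaplan-Meier plots. Section 5.2.4 names the amount of actual use as the limit on this subgroup. It does not mention selection by survival or tolerance.

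**The concern.** Age, sex and lymphoma type are known at baseline. The number of cycles finally received is not: it depends on the patient surviving and tolerating treatment. Someone classed as having more than 16 cycles cannot have died, or had an event that ended treatment, before cycle 17. If events and time are counted from first dose, those 16 cycles enter the denominator as immortal time, and the treatment-ending events of cycles 1–16 all fall in the other group.

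Events that do not end treatment suffer differently. The group's figure mixes cycles 1–16 with later cycles, so a change after cycle 16 is diluted. The proportion with an event rises simply because exposure is longer.

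At stake is a question the protocol itself poses: whether the safety profile changes beyond the exposure seen in the pivotal studies.

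**Working it through.** **The plan's own figure.** None is given for this group. Table 2, the only calculated precision, concerns proportions in all 500 patients. Its 5% row reproduces as 0.05 ± 1.96·√(0.05·0.95/500) ± 1/1000 = 2.99% to 7.01%. It does not bear on this point.

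**Inputs.** From the protocol: the cut at 16 cycles, the clock from first dose, and a median of 9 cycles (the phase 2 HL study, section 1). Assumed: a constant chance of stopping per cycle; h = 0.06 events per cycle; a share f of events ends treatment; equal risk for all patients; the hazard from cycle 17 multiplied by m = 1 or 2; other stopping unchanged after cycle 16. Time is counted in cycles, without the 30-day tail.

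**Retention.** Staying per cycle S = 0.5^(1/9) = 0.9259, so stopping q = 0.0741. The share beyond 16 cycles is S^16 = 0.292. The mean number of further cycles is M = 1/q = 13.49, so the group's mean total is 29.49.

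**Cycles 1–16.** All patients contribute (1 − S^16)/q = 9.556 cycles per treated patient. Of these, 16 × 0.2916 = 4.666 belong to the >16 group and 4.890 to the ≤16 group. The >16 group's rate in these cycles is e = h(1 − f)/(1 − hf).

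**Group rates from first dose.**
- ≤16 group: (h·9.556 − e·4.666)/4.890
- >16 group: (16e + M·m·h)/(16 + M)
- With doubling, event-related stopping also doubles: 1/M = 1 − (1 − o)(1 − 2hf), with 1 − o = S/(1 − hf)

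Example, f = 0.3 and no change: e = 0.042/0.982 = 0.0428. The ≤16 rate is (0.5734 − 0.1996)/4.890 = 0.0764. The >16 rate is (0.684 + 0.809)/29.49 = 0.0507. The ratio is 0.66.

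Rates per 100 cycles:

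| f | e | ≤16 rate | >16 rate, no change | Ratio (true 1.0) | M if doubled | >16 rate, doubled | Ratio (true 2.0) |
|---|---|---|---|---|---|---|---|
| 0 | 6.00 | 6.00 | 6.00 | 1.00 | 13.49 | 8.74 | 1.46 |
| 0.1 | 5.43 | 6.54 | 5.69 | 0.87 | 12.54 | 8.32 | 1.27 |
| 0.3 | 4.28 | 7.64 | 5.07 | 0.66 | 10.98 | 7.42 | 0.97 |
| 1.0 | 0 | 11.73 | 2.74 | 0.23 | 7.51 | 3.83 | 0.33 |

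**Incidence proportions, f = 0.3, no change.** In the >16 group, 1 − ((1 − h)/(1 − hf))^16 · p0, with o = 0.0572 and p0 = (1 − h)o/(1 − (1 − h)(1 − o)) = 0.473. This gives 1 − 0.497 × 0.473 = 76.5%. In the ≤16 group the same model gives about 43%. The long-term group looks worse on this measure. At f = 1 the two proportions are about equal.

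**Sensitivity to the assumed tail.** For events that always end treatment, at constant risk, the >16 rate is (mean − 16)/mean of the truth: 13.49/29.49 = 46% here, 5/21 = 24% if the group averages 21 cycles, and 2/18 = 11% if it averages 18.

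**Splitting time at cycle 17.** With equal risk, events per cycle from cycle 17 over events per cycle in cycles 1–16 of all patients returns the true ratio at every f. By simulation it is 0.99–1.00 when the truth is 1.0 and 1.99–2.01 when it is 2.0. With unequal risk (assumed gamma frailty, variance 1, true within-patient ratio 1.0) it gives 0.73 at f = 0.3 and about 0.4 at f = 1. The split removes the immortal time but not the selection.

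**Same patients, earlier against later cycles.** With all events counted at f = 0.3 and no true change, the ratio is 6.00/4.28 = 1.40, because their early cycles cannot contain treatment-ending events. With those events left out on both sides it is 4.20/4.28 = 0.98.

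**The case against.** The protocol sets no clock specifically for this subgroup. The synopsis leaves time at risk to the SAP, 5.2.1 makes the subgroup optional, no formal testing is planned, and no comparison of >16 with ≤16 cycles is named. A SAP could add a later start. This lowers the severity. It does not remove the point: 4.4.1 fixes the population, 5.2.2.1 fixes the only clock, and a SAP that follows both inherits the problem. Descriptive subgroup tables will also be read side by side.

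Section 1 describes neuropathy, neutropenia and infusion reactions as mostly managed by dose delay or reduction, so f may be small for those events. That stands. At f = 0 there is no downward bias in the rates, only dilution.

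Long-term use is not among the objectives in section 3, and the overall estimates and the neuropathy model do not depend on this subgroup. That stands too.

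A reader might infer that the plan makes long-term use look safe on every measure. It does not, since incidence proportions generally move the other way. A reader might also infer that the study cannot reveal late risk at all. That is too strong: cycle data and onset dates are collected, and the display by completed cycles could show it, though only for selected events and with no stated link to the long-term question.

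**Conclusion.** The point holds and is a should-fix. As written, incidence rates in the >16-cycle group carry 16 cycles of immortal time for fatal and treatment-ending events, late changes are diluted, and proportions are generally inflated by exposure. Neither headline measure answers the question set in sections 1 and 2.

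The direction of the rate bias requires only that some events end treatment or life. Its size rests on the assumed retention, hazard and f. Under those assumptions a true doubling after cycle 16 nearly vanishes (0.97) when 30% of events end treatment. The ratio of 0.23 is the extreme at which every event does, and should not be taken as typical. The protocol gives no data on retention beyond cycle 16, so the tail is the weakest assumption.

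**What to change.** - In 4.4.1, 5.2.1 and the synopsis, keep the >16-cycle group as a description only.
- Report long-term rates from events and person-time starting at the cycle-17 dose and ending at last dose plus 30 days, among patients who started cycle 17. Allocate every treated patient's events and time to the cycle band in which they occur.
- State that patients who reach cycle 17 are selected for survival and tolerance, so a comparison with earlier bands of all patients can still look reassuring.
- For events that do not end treatment, add a comparison with the earlier cycles of the same patients, leaving treatment-ending events out on both sides. Interpret treatment-ending events as absolute rates after cycle 16.
- Reconcile the cut-off: section 2 includes patients with exactly 16 cycles, whereas 4.4.1, 5.2.1 and 5.2.4 do not. The start of the long-term clock must match the cut-off chosen.

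The cost is wording and programming, because cycle and onset dates are already recorded. The long-term estimate will rest on fewer events and have a wider interval. Under constant stopping, about 146 of 500 patients (0.292 × 500) would contribute at a median of 9 cycles. About 79 (0.5^(16/6) = 0.157, × 500) would do so at a median of 6, the sALCL figure in section 1.

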4.4.2 Effectiveness measures

The focus of this study is safety; therefore no measures or analyses regarding treatment effectiveness are included in the study.

4.4.3 Other measures

All dose modifications including dose delays, temporary interruptions and permanent interruptions, and reported reason for change(s) will be summarised, and where possible the effect of modifications on safety will be explored.

4.5 Data Collection

4.5.1 Schedule of Recommended Recording of Essential Data

Essential data for the study are presented in the Schedule of Recommended Recording Essential Data provided in Table 1. For eligible patients who provide informed consent, data elements will be abstracted from information routinely recorded in the medical record. Follow-up data will be collected in conjunction with all routine care visits, typically occurring at approximately every three months. No study visits or examinations, laboratory tests or procedures are mandated as part of this study.

Confidential. Page 19 of 44

Table 1 Schedule of Recommended Recording of Essential Data

	Enrolmenta	On-Treatment Follow- up ^b	Post-Treatment Follow-up ^c (or study discontinuation)
Informed consent	X		
Demography	X		
Patient height & weight	X	X (weight only)	
ECOG Performance Status	X	X	
Relevant medical history & co-morbidities	X	X	
Laboratory test results (if performed as part of routine care)	X	X	
Relapsed or refractory CD30+ HL or sALCL disease and treatment history	X	X	
Brentuximab vedotin treatment details	X	X	
Concomitant medications	X	X	
Changes in treatment, including dose modifications		X	
Survival status			X
SAE and AESI recording in eCRF (Refer to section 7.2) ^d	X	X	
Both SAEs and AESI considered related to brentuximab vedotin - recording in eCRF (Refer to Section 7.2) ^d			X
Date and reason for discontinuation (if applicable)		X ^e	X ^e

^a Exposure to brentuximab vedotin may have started prior to enrolment. All brentuximab vedotin treatment and concomitant medication exposures, SAEs/AESI and relevant medical history since starting the current brentuximab vedotin regimen should be recorded at the time of enrolment.

4.5.2 Baseline/Enrolment

The following data will be recorded, where available, at baseline for all enrolled patients:

- Demographics [date of birth, sex, race/ethnicity (where allowed by local regulations)]
- Weight, height (calculated BMI)
- ECOG performance status
- Relevant medical history, including cardiovascular (e.g., congestive heart failure, rhythm abnormalities), diabetes, pulmonary (e.g., chronic obstructive pulmonary

Confidential. Page 20 of 44

^b The On-Treatment period is defined as beginning at the time of enrolment and continuing through 30 days after the last dose of brentuximab vedotin.

^c The Post-Treatment Follow-up period is defined as beginning 31 days after the last dose of brentuximab vedotin and continuing until study discontinuation.

^d Refer to Section 7.2 for the procedures for recording and reporting SAEs and both serious and non-serious, AFSIs

^e Refer to section 4.5.4 for a listing of data to be recorded at the time of study discontinuation.

disease), hepatic, renal, other malignancies, neurologic (e.g., neuropathies), autoimmune disease, infectious disease (e.g., HIV, Epstein Barr virus), abnormal blood counts (cytopenias and growth factor exposure), thyroid dysfunction

- Relevant laboratory testing [e.g., haematology, lactate dehydrogenase (LDH), CD30 expression %], if performed as part of routine care
- CD30+ HL or sALCL disease and treatment history
 - o Disease type (CD30+ HL or sALCL)
 - o Date of initial diagnosis
 - Diagnostic testing performed
 - o Disease stage
 - Presence of lymphoma-related symptoms (B symptoms)
 - o Extent of disease determined by both physical examination and imaging
 - o ALK status (positive, negative, unknown) (sALCL patients only)
 - o ALCL variant: common, small cell, lymphohistiocytic, sarcomatoid, other, unknown (sALCL patients only)
 - o HL subtype: nodular sclerosing, mixed cellularity, lymphocyte-rich, lymphocyte depleted, unspecified/unknown
 - o Previous treatment
 - Previous lines of therapy, with number of cycles
 - Autologous stem cell transplant or allogeneic stem cell transplant
 - Radiation therapy
- Brentuximab vedotin treatment, including dose and treatment date for current regimen and any changes in treatment dose prior to enrolment
- Occurrence of SAEs and both serious and non-serious AESI (per Section 7.2 Procedures for Recording and Reporting SAEs and AESI) since start of current treatment regimen of brentuximab vedotin
- Concomitant medications

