4. STUDY DESIGN

4.1 Study Description

This is a multi-center international prospective, observational cohort study of patients who have been diagnosed with relapsed or refractory CD30+ HL or relapsed or refractory sALCL and are treated with brentuximab vedotin as part of routine clinical care. The study will target the enrolment of approximately 500 patients (at least 50 of whom have a diagnosis of sALCL), who are initiating or are currently being treated with brentuximab vedotin at approximately 75-100 sites in 12-15 countries in Europe and potentially in other countries outside of Europe. Patients already being treated with brentuximab vedotin at the time of enrolment will be considered to be retrospectively enrolled for purposes of analysis and inclusion in the PASS. The sample size for this study was based on the need for more information regarding the occurrence of both serious and non-serious AESI, relative to the

Confidential. Page 15 of 44

size of the current safety database. The study will continue for five years from the date of first patient enrolled. The study will be managed by the contract research organization (CRO) Quintiles, with oversight by Millennium Pharmaceuticals, Inc. (Millennium) project team.

Sites that treat patients with relapsed or refractory CD30+ lymphomas including HL and sALCL will be invited to participate in the study. Country and site selection will depend on the timing of commercial availability of brentuximab vedotin, reimbursement status, and physician product adoption rates in the selected countries to ensure that an adequate number of patients treated with brentuximab vedotin are available for enrolment into the study. The duration of the enrolment period may be extended (or contracted) based on actual patient accrual rates.

Eligible patients will be identified from sites where patients are initiating or already receiving therapy with brentuximab vedotin. No study specific visits or procedures will be required as part of patient participation in the study. Patients will be evaluated according to the physician's standard practice and discretion.

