5. STATISTICAL METHODS

5.1 Sample size

The sample size for this study was chosen to provide better evaluation of the both serious and non-serious AESI, given the size of the current safety database. Evaluation of the sample size for the study was performed based on the expected rate of AESI in patients with relapsed or refractory CD30+ HL or relapsed or refractory sALCL treated with brentuximab vedotin to ensure sufficient enrolment in the study.

Table 2 shows the estimated 95% CIs for given frequencies of AESI from a study population of 500 patients which was calculated using an appropriate model for proportions, assuming a normal approximation to the binomial distribution. The targeted sample size of 500 (at least 50 of whom have a diagnosis of sALCL), provides an adequate level of precision to achieve the objectives of this study related to AESI, through estimating the proportion of patients with each individual AESI. The sample size of 500 includes the patients already being treated with brentuximab vedotin at the time of enrolment, the retrospective patients. It is assumed that approximately 15 to 20% (75 to 100 patients) of the study population will be retrospectively enrolled.

Confidential. Page 22 of 44

Table 2. Incidence Proportion and 95% Confidence Intervals for AESI

Proportion	Number of Events	95% Confidence Interval
0.00	0	(0.0%, 0.7%)
0.01	5	(0.0%, 2.0%)
0.02	10	(0.7%, 3.3%)
0.03	15	(1.4%, 4.6%)
0.04	20	(2.2%, 5.8%)
0.05	25	(3.0%, 7.0%)

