5.2 Data Analyses

5.2.1 General Considerations

All SAEs and AESI (including both serious and non-serious AESI) verbatim terms will be recorded and coded using MedDRA. The severity of adverse events will be graded utilizing NCI CTCAE v4.03. All computations and generation of tables, listings and figures will be performed using SAS[®] version 9.2 or higher (SAS Institute, Cary, NC, USA). No formal hypothesis or statistical significance testing is planned. This approach follows the Guidelines for Good Pharmacoepidemiology Practices, Section D, point 10.

Details of the statistical analysis will be fully described in a written and approved statistical analysis plan (SAP). Descriptive analyses will be performed to gain an understanding of the qualitative and quantitative nature of the data collected and the characteristics of the sample studied. Descriptive statistics will be reported for all measured variables captured in this study. Summary statistics for continuous variables to be reported will include N, mean, median, standard deviation, 95% confidence interval (CI) and range. Skewed variables may be log-transformed or classed into quantiles of the distribution and analyzed as a categorical variable. Categorical variables will be reported using counts and proportions.

Analyses will be conducted on the entire enrolled population, including all patients exposed to brentuximab vedotin. In addition, analyses will be presented separately for patients prospectively and retrospectively enrolled to account for potential differences in the data reported, in particular the volume and nature of adverse events. Analyses by cohort will include disease history, ECOG performance status, and other background information to determine whether there are baseline differences between groups which could influence the safety results.

Because information collected is routinely recorded in medical records, it is expected that nearly all the data collected for the prospective cohort will also be available for the retrospective cohort. In addition, SAEs and the AESIs, in general, are events that should also be captured in patient records. However, to formally address the concern for completeness of

Confidential. Page 23 of 44

data for the retrospective cohort, where possible, the number and percentage of missing data items will also be tabulated and compared between the two cohorts.

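### Baseline is tied to enrolment while risk time runs from first dose, so for the 75–100 retrospective patients baseline items that change on treatment may be post-exposure values

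*Protocol*

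**What the plan says.** Protocol Section 4.1 defines the retrospective cohort: "Patients already being treated with brentuximab vedotin at the time of enrolment will be considered to be retrospectively enrolled". Section 5.1 counts these patients within the 500 and gives their expected number: "It is assumed that approximately 15 to 20% (75 to 100 patients) of the study population will be retrospectively enrolled".

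Section 4.5.2, under the joint heading Baseline/Enrolment, states: "The following data will be recorded, where available, at baseline for all enrolled patients". The list covers weight and height, ECOG, laboratory tests and medical history, with neuropathies as an example. It also covers treatment changes made before enrolment and events since the regimen began, so the record is plainly taken as of enrolment. Table 1, footnote a (Section 4.5.1), acknowledges the consequence: "Exposure to brentuximab vedotin may have started prior to enrolment". It adds that treatment, concomitant medication, events and "relevant medical history since starting the current brentuximab vedotin regimen should be recorded at the time of enrolment". Footnote b starts the on-treatment period at enrolment.

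Other sections use first dose as the reference. Section 5.2.2.1 counts time at risk from first dose to last dose plus 30 days. Section 7.2.1 records events from first dose. Section 7.1 judges pre-existing conditions against the time before administration.

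Two analyses use the baseline data. Section 5.2.1 says: "Analyses by cohort will include disease history, ECOG performance status, and other background information to determine whether there are baseline differences between groups". Section 5.2.2.1 plans a Cox model for "risk factors for peripheral neuropathy (e.g., BMI, previous history of neuropathy, known toxic exposures) in the cohort".

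**The concern.** Outcomes are anchored at first dose and baseline covariates at enrolment. The two dates are close for a patient who enrols when starting treatment. They differ for anyone already on the drug.

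This matters in two places. The first is the cohort comparison, which the amendment log says was added to answer a regulatory concern about differences between the cohorts. For ECOG, weight and laboratory values it may set on-treatment status in one cohort against pre-treatment status in the other. A difference could then reflect the drug rather than who was selected, and a true selection difference could be hidden.

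The second is the study's second objective, risk factors for neuropathy. If an on-treatment neuropathy is entered as medical history at enrolment and also as an event, the outcome leaks into the covariate and pushes its hazard ratio up. BMI, another named candidate, has the weaker problem that its baseline value may be a post-exposure one.

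**Working it through.** **1. The protocol's own figures.** 0.15 × 500 = 75 and 0.20 × 500 = 100 retrospective patients, as stated. The non-zero rows of Table 2 follow from p ± 1.96√(p(1−p)/500) ± 1/(2×500). At 1% this is 0.01 ± 0.0087 ± 0.001, or 0.03% to 1.97%, printed as 0.0% to 2.0%. The zero row is the exact limit, 1 − 0.025^(1/500) = 0.74%. None of these figures depends on how baseline is defined, so the sample-size justification is untouched.

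**2. Which reference date each element uses.**

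| Element | Reference date | Place |
|---|---|---|
| Weight, ECOG, laboratory values, medical history at baseline | Enrolment | 4.5.2, Table 1 |
| Start of on-treatment period | Enrolment | Table 1, footnote b |
| Time at risk | First dose | 5.2.2.1 |
| Event recording | First dose | 7.2.1 |
| Pre-existing conditions | First administration | 7.1 |

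Footnote a reaches back to regimen start for treatment, concomitant medication, events and history. It does not do so for weight, ECOG or laboratory values, and no section asks for the last value before first dose.

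**3. Size of a possible neuropathy bias.** From the protocol: N = 500; 75 or 100 retrospective patients; about half of phase 2 patients with neuropathy; median exposure about 27 weeks in HL and 20 weeks in sALCL (Section 1).

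Assumed, not in the documents: exponential time to neuropathy with median 27 weeks (hazard ln 2/27 = 0.0257 per week); exponential treatment duration with median 27 weeks and a 3-week minimum; enrolment uniform over each retrospective patient's own treatment time; true prior neuropathy in 20%. The model is a Cox regression on history alone, with 1,000 simulated cohorts per row.

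About 31–33% of retrospective patients then have onset before enrolment: 0.31 × 75 ≈ 23 to 0.33 × 100 = 33 patients, or about 5–7% of 500. The estimated hazard ratio by share of those onsets recorded as history is:

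| Share recorded as history | True HR 1.0 (75 / 100 retrospective) | True HR 1.5 (75 / 100 retrospective) |
|---|---|---|
| 0% | 1.00 / 1.00 | 1.51 / 1.50 |
| 10% | 1.03 / 1.04 | 1.54 / 1.55 |
| 25% | 1.07 / 1.09 | 1.57 / 1.59 |
| 50% | 1.15 / 1.19 | 1.65 / 1.70 |
| 100% | 1.29 / 1.39 | 1.79 / 1.90 |

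A second set of assumptions used 30% prior neuropathy, hazard 0.026 per week, treatment capped at 48 weeks plus 30 days, and about 36% with onset before enrolment. For a true HR of 1.0 it gave 1.12 / 1.17 at 50% and 1.23 / 1.33 at 100%. Taken together, the ranges are 1.03–1.04 at 10% (first set only), 1.12–1.19 at 50% and 1.23–1.39 at 100%. With history fixed at first dose, the estimates return to the true values.

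**4. Scale against sampling error.** SE(log HR) ≈ 1/√(D·q(1−q)). With D = 250 events and q = 0.20, this is 1/√40 = 0.158. The 50% case in the table, ln 1.15 to ln 1.19 = 0.140 to 0.174, is about one standard error.

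**The case against.** The strongest reply is that the protocol already holds what is needed to keep history and outcome apart. Section 4.5.2 lists medical history and events since regimen start as separate items. Section 7.2.1 requires an onset date for each event, treatment dates are recorded, and Section 7.1 uses first administration as the reference for pre-existing conditions. Section 5.2.2.1 leaves the choice of covariates to the SAP. Footnote a can also be read as giving a place to data from the gap between first dose and enrolment, not as turning them into baseline covariates. Contamination then needs a double entry and an analysis that ignores onset dates. This stands: the neuropathy bias is possible, not built in.

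A reader might go further and infer that retrospective patients typically enrol after several cycles and after neuropathy onset. The protocol gives no time from first dose to enrolment, so this has no support. Nor are the changeable items collected only once: Table 1 and Section 4.5.3 repeat weight, ECOG, history and laboratory values during follow-up. Only the baseline value is single.

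The reply does not dispose of ECOG, weight and laboratory values. A SAP can choose covariates, but it cannot recover pre-dose values that the eCRF did not request. Section 5.2.1 expects nearly all data to be available in both cohorts; that concerns completeness, not timing. Section 4.5.2 also lists no onset date for history items, so separating earlier from on-treatment neuropathy is not assured.

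**Conclusion.** The point holds in a bounded form. The protocol uses two time origins. As written, it allows post-exposure values of ECOG, weight/BMI and laboratory tests to stand as baseline for 75–100 of 500 patients. For those items the cohort comparison lacks a common reference time.

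A reader might infer that the whole comparison fails. It does not: sex, diagnosis date, subtype, ALK status and prior lines do not depend on when the patient enrolled. The 400–425 prospective patients, who are also presented separately, lie outside the mechanism.

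For the neuropathy model, upward bias is a risk rather than a certainty. It ranges from nil, through about 1.03–1.04 at 10% misrecording, to 1.23–1.39 at 100%, for a true hazard ratio of 1.0. These figures rest on about one third of retrospective patients having onset before enrolment, and on assumed prior-neuropathy prevalence, time distributions and a single-covariate model. The documents do not say what misrecording share to expect. The change should be made, but no stated sample-size or precision figure depends on it.

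**What to change.** In Section 4.5.2 and Table 1:

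- Define baseline for both cohorts as the last recorded value on or before the first dose of the current regimen, taken from the medical record and entered with its date.
- Label later values of retrospective patients, including those from the enrolment date, as on-treatment data.
- Count neuropathy as history only if its onset precedes that first dose, and reword footnote a so that a later neuropathy is entered as an event only.
- Use these pre-dose values in the cohort comparison of Section 5.2.1 and the Cox model of Section 5.2.2.1.

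The cost is a definition, a date field and a line in the eCRF completion guideline; the source record is the same. The downside is that some pre-dose values will be missing for retrospective patients. The missing-data tabulation by cohort already planned in Section 5.2.1 would make that visible, and a missing value is preferable to a mislabelled one.
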